5.3.4 Assessment of Causality of Adverse Events

Investigators should use their knowledge of the participant, the circumstances surrounding the event, and an evaluation of any potential alternative causes to determine whether an adverse event is considered to be related to the study drug, indicating "yes" or "no" accordingly. The following guidance should be taken into consideration:

- Temporal relationship of event onset to the initiation of study drug
- Course of the event, with special consideration of the effects of dose reduction, discontinuation of study drug, or reintroduction of study drug (as applicable)
- Known association of the event with the study drug or with similar treatments
- Known association of the event with the disease under study
- Presence of risk factors in the participant or use of concomitant medications known to increase the occurrence of the event
- Presence of non-treatment-related factors that are known to be associated with the occurrence of the event

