### STATISTICAL ANALYSES

#### 5.1 GENERAL CONSIDERATION

The purpose of this study is to assess the safety, tolerability, and efficacy of long-term administration of open-label gantenerumab in participants with AD who completed GRADUATE I or GRADUATE II.

The period of the POSTGRADUATE study and the OLE period from the parent studies will henceforth be referred to as the OLE period. Data from the OLE period, i.e., from OLE baseline (see Section 5.1.1 below for definition) to the end of study, will be summarized. Consequently, for participants who completed the OLE part of the parent studies and gave informed consent for the POSTGRADUATE study, the data collected in the OLE period of the parent studies will be included in the CSR of POSTGRADUATE. This will ensure that data from baseline and uptitration are included in the analyses for all participants of POSTGRADUATE. Participants of the OLE period of the parent studies without informed consent to POSTGRADUATE cannot be included in the analyses for the CSR of POSTGRADUATE and will instead be included in the analyses within the parent studies' CSRs.

All analyses will be purely descriptive and no imputation of missing data will be performed. For continuous data, descriptive statistics of mean, standard deviation, median, 1st and 3rd quartile as well as minimum and maximum and number of available data will be provided. For categorical data, number and frequency will be provided for each category as well as the number of available data.

All analyses of safety endpoints will be based on the SE analysis set unless mentioned otherwise while all analyses of efficacy endpoints will be performed for the ITT analysis set. The immunogenicity analysis set will be used for immunogenicity analyses.

Results will be shown separately based on previous treatment in the GRADUATE parent studies GRADUATE I and GRADUATE II, and by participation / non-participation in the OLE part of the parent studies and overall. For analyses using the ITT analysis set, this will be the treatment as randomized in the parent studies; for analyses using the SE analysis set, this will be the treatment actually received in the parent studies.

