### 5.3.3 Adverse Events

All verbatim AE terms will be coded using the Medical Dictionary for Regulatory Activities (MedDRA) version that is current at the time of the analysis (Version 25.0 or higher), and AE severity will be graded according to the scale defined in Table 3 in Section 5.3.3 of the study protocol (mild/moderate/severe). For each displayed participant group, the frequency of each AE preferred term will be defined as the number of participants experiencing at least one occurrence of the event. Each table will present the overall number and percentage of participants experiencing at least one AE and the total number of AEs reported. Percentages will be based on the number of participants in the SE analysis set. In summary tables, AEs will be sorted by body system (in decreasing order of overall incidence), then by preferred term (in decreasing order of overall incidence). The summary tables will be restricted to treatment-emergent AEs, i.e., AEs that occur or worsen on or after the day of first OLE dose, with onset no later than 14 weeks after last dose. Non-treatment-emergent AEs (AEs ongoing at OLE Day 1 with onset before the first OLE dose) and AEs occurring more than 14 weeks after the last dose will be listed.

The following safety information will be summarized:

- AEs, AEs by intensity, AEs related to study drug
- AEs with fatal outcome

- Serious AEs (SAEs), SAEs by intensity, SAEs related to study drug
- AEs leading to discontinuation of study treatment
- AEs leading to dose modifications (dose interruption, dose reduction, or delayed uptitration). Delayed up-titration at any given visit is defined as the simultaneous occurrence of the following two tickboxes in the eCRF Adverse Event form:
  - Action taken with open label gantenerumab due to SAE/AE: Dose Not Changed
  - If Dose not changed, was open label dose regimen modified from protocol schedule due to SAE/AE? Yes
- Injection site reaction (ISR) signs and symptoms
- Systemic injection reactions (AEs with "systemic reaction" selected)

Protocol-specified adverse events of special interest (AESI) will be listed.

The impact of the COVID-19 pandemic on the safety data will be assessed by reviewing the following:

- Confirmed or suspected COVID-19 AEs
- AEs associated with COVID-19
- Potential long COVID-19 symptoms

The following data handling rules will be applied for all AE summary tables:

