- Events that are missing both onset and end dates will be considered to have started after the first dose of study drug and the duration will be set to missing.
- If the onset date is missing, and the end date is on or after the first dosing date or unresolved or missing, then the event will be considered to have started after the first dose of study drug.

The following data handling rules will also be applied for specific tables:

- An AE will be included in the summary table of AEs leading to study drug discontinuation if the "action taken with open label gantenerumab" drop-down menu on the AE eCRF is checked "drug withdrawn".
- In the summary table of AEs by intensity, if a participant has more than one
  occurrence of an event, the event with the most severe intensity will be counted. If
  the intensity of an AE is missing, then the AE will be included only in the total
  number of events column, and not in the count of participants with the event by
  intensity.
- In the summary table of AEs related to study drug, if a participant has more than
  one occurrence of an event, the related event will be counted if applicable. If the
  relationship of an AE is missing, then the AE will not be included in the count of
  participants with the event by relationship

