#### 5.8 INTERIM ANALYSES

### 5.8.1 Planned Interim Analyses

A first interim analysis will be conducted at the time of the primary analysis for the parent pivotal studies GRADUATE I and GRADUATE II, to support a potential filing of gantenerumab in case of positive read-out of the pivotal studies. A second interim analysis may be conducted for an update on safety data in the filing dossier. The analyses will be strictly descriptive and will not impact the conduct of the study, i.e., early termination for futility or efficacy will not be considered. As this study is open-label and all analyses are descriptive, the interim analyses are considered of an administrative nature and will not have an impact on the final study results.

The following will be included in the interim analyses:

- Participant disposition (see Section 5.2)
- Demographics and baseline characteristics (see Section 5.7.2)
- Extent of exposure (see Section 5.6.1)
- Adverse Events (see Section 5.3.3)
- MRI safety findings (see Section 5.3.4, excluding analyses of time to onset or time to recurrence of ARIA, and analyses by dose level. Not all analyses will be run by APOE ε4 genotype.)
- Laboratory data (see Section 5.3.5)
- Vital signs (see Section 5.3.6)
- ECG data (see Section 5.3.7)
- C-SSRS data (see Section 5.3.8)

Immunogenicity analyses may also be performed at the interim analysis.

No interim analyses of efficacy data will be done.

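### Dropping AEs with missing causality from the related-AE count makes the reported related rate a lower bound, and the SAP does not plan to show it as one

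*SAP*

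**What the plan says.** The planned safety summaries in SAP 5.3.3 include "AEs, AEs by intensity, AEs related to study drug" and "Serious AEs (SAEs), SAEs by intensity, SAEs related to study drug". Each preferred term is counted by participants with at least one occurrence, and "Percentages will be based on the number of participants in the SE analysis set".

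The data handling rules at the end of SAP 5.3.3 deal with missing fields:

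- **Relationship.** In the table of AEs related to study drug, a participant with several occurrences of an event is counted if one of them is related. If the "relationship of an AE is missing, then the AE will not be included in the count of" participants with the event by relationship. The section specifies no missing row, footnote, listing or alternative count for such events.
- **Intensity.** If "the intensity of an AE is missing, then the AE will be included only in the total" number-of-events column. It is left out of the participant counts by intensity but stays visible in that total.
- **Onset date.** An event with no onset date and no end date is taken to have started after first dose. So is one with no onset date whose end date is on or after first dosing, unresolved or missing.

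SAP 5.1 adds a general rule: "All analyses will be purely descriptive and no imputation of missing data will be performed".

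On collection, Protocol 5.3 requires the investigator to assess seriousness, severity and causality for each AE recorded on the eCRF. Protocol 5.3.4 makes the causality answer a plain yes or no.

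**The concern.** Safety is the primary objective, and the related-AE and related-SAE tables are among its planned outputs. An event whose relationship was never recorded drops out of the numerator, while its participant stays in the denominator. In the percentage it therefore counts the same as an event judged unrelated, and nothing in the table tells the reader that this has happened. A figure that is by construction a lower bound would be read as the rate.

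The AE analyses of SAP 5.3.3 also feed the interim analyses, which support a possible filing, and "A second interim analysis may be conducted for an update on safety data in the filing dossier" (SAP 5.8.1). The same tables could therefore be read outside the study report.

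**Working it through.** The plan states no related-AE rate and no missing proportion, so there is no figure to reproduce. The check covers direction first, then an illustration of size.

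**Direction.** Take the recorded relationships as correct. For a given table let

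- N = participants in the SE set, fixed by SAP 5.3.3
- A = participants with at least one AE recorded as related
- T = participants who would have at least one related AE if no relationship were missing
- M = participants with at least one AE of missing relationship and none recorded as related

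Everyone in A is also in T. Anyone in T but not in A must have a missing-relationship AE and none recorded as related, so belongs to M. Hence

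A/N ≤ T/N ≤ (A + M)/N.

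The SAP rule reports A/N, the lower bound. Counting the missing as related gives (A + M)/N, the upper bound. SAP 5.1 rules out imputation, so a missing relationship has no route into A.

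A simulation agrees: 1000 data sets of 300 participants, with missingness allowed to differ between related and unrelated AEs. The SAP count minus the true count ranged from -50 to 0 and was exactly 0 in 41 data sets. The count with missing treated as related was never below the true count.

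**Related SAEs.** The missing-relationship rule names only the table of AEs related to study drug. SAEs are AEs, the related-SAE summary is listed in the same section, and SAP 5.1 allows no imputation. The same inequality therefore follows, but by inference.

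**Size, participant level.** Assume one event per participant, a related rate p, and a share m of AEs with missing causality. Then the reported rate is p(1 - m), the shortfall is p × m, and the participants lost are N × p × m. N = 2032 is the enrolment ceiling (SAP 3); p and m are assumed.

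| p | m | Reported rate | Shortfall (points) | Participants lost |
|---|---|---|---|---|
| 1% | 0.5% | 0.995% | 0.005 | 0.1 |
| 1% | 2% | 0.98% | 0.02 | 0.4 |
| 5% | 5% | 4.75% | 0.25 | 5.1 |
| 20% | 2% | 19.6% | 0.4 | 8.1 |
| 20% | 10% | 18.0% | 2.0 | 40.6 |

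The loss is smaller when participants have another occurrence recorded as related, because the SAP still counts them.

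**Which bound lies nearer the truth.** Work in shares of AEs and assume that 20% of all AEs are related, the unassessed ones included:

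- m = 1%: the SAP rule gives 0.20 × 0.99 = 0.198, an error of -0.2 points. Missing counted as related gives 0.198 + 0.01 = 0.208, an error of +0.8 points.
- m = 3%: the SAP rule gives 0.20 × 0.97 = 0.194, an error of -0.6 points. Missing counted as related gives 0.194 + 0.03 = 0.224, an error of +2.4 points.

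Under these assumptions the upper bound errs four times as far as the lower. These are event shares and do not measure the participant tables.

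**The case against.** The strongest reply is that little is lost. Causality is mandatory and binary for every recorded AE (Protocol 5.3 and 5.3.4). Available SAE details must be entered within 24 hours (Protocol 5.4.2), expedited reporting relies on the investigator's causality assessment (Protocol 5.7), and discrepant data are queried (Protocol 7.1). Missing values should be few, especially for SAEs. Affected events remain in the all-AE and all-SAE tables, and in the fatal, discontinuation and dose-modification summaries where they apply. The study is descriptive and tests no hypothesis (SAP 2). All of this stands, and it makes the point minor.

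Four stronger readings are tempting, and the documents do not support them.

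- A reader might infer that missing causality should simply be imputed as related. On the assumptions above that errs further than the SAP rule, in the other direction, and it departs from the no-imputation statement in SAP 5.1.
- A reader might infer that missing fields cluster at the interim data cuts. Nothing in either document says so, and the collection rules suggest otherwise.
- A reader might see a contradiction with the onset-date rule. The date rule decides whether an event enters the treatment-emergent tables at all; the relationship rule decides one attribute within a table. They lean in different directions but answer different questions.
- A reader might infer that the net effect of all the rules is downward. The date rule can bring events into the tables, so the direction shown here belongs to the relationship rule alone.

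The reply does not remove the lack of visibility. For missing intensity the SAP keeps the event in a total column; for missing relationship it states nothing comparable.

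**Conclusion.** The point holds as a minor one. Through the missing-relationship rule alone, the related-AE rate planned in SAP 5.3.3 is a lower bound: its error is zero or downward. It is zero when the unassessed event was in fact unrelated or when the participant has another occurrence recorded as related. This rests on the fixed SE denominator and on taking recorded relationships as correct. For related SAEs the conclusion is inferred, and the SAP should state the rule for them explicitly.

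The actual size cannot be computed from the documents and is probably small. The range of 0.005 to 2.0 percentage points depends wholly on the assumed p and m. The missing-intensity rule is a weaker instance of the same reporting gap, since those events stay in the total.

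**What to change.** Replace the missing-relationship rule in SAP 5.3.3, for both the related-AE and the related-SAE table, with wording such as:

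*For each event, participants with at least one occurrence of missing relationship and no occurrence recorded as related will be shown in a separate 'relationship missing' row. The related count will also be given with these participants counted as related (upper bound).*

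In the by-intensity table, add a missing category for participants who have the event but no occurrence with a recorded intensity.

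The cost is one extra row per table and a sentence or two of SAP text, with no new data and no change to study conduct. The upper-bound figure will overstate relatedness if the missing events are mostly unrelated, so it should be labelled as a bound. SAP 5.1 should note it as an alternative display, so that it does not conflict with the no-imputation statement. If nothing is missing, the row shows zero.

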### 5.3.4 Magnetic Resonance Imaging Safety Findings

ARIA-E and ARIA-H are identified risks associated with gantenerumab. Sites were asked to capture ARIA findings as AEs in the POSTGRADUATE eCRF if they met any of the following criteria:

- Symptomatic ARIA-E (onset or worsening of CNS symptom[s] attributable to ARIA-E MRI findings in the judgement of the investigator), and/or
- ARIA findings that result in a change in study treatment (e.g., dosage modification, treatment interruption, or treatment discontinuation), and/or
- · Findings that are otherwise clinically significant in the investigator's judgment

Not all ARIA MRI findings qualify as AE. ARIA analyses will be mainly based on ARIA MRI findings. ARIA AEs will also be reported. ARIA analyses will be restricted to ARIAs documented during this study or the OLE part of the parent studies.

Based on MRI data, the incidence, severity (based on the Bioclinica severity scale (see Appendix 2) and the Barkhof Grand Total Score [BGTS]) and timing of ARIA-E and the incidence and timing of ARIA-H will be summarized overall and also by APOE  $\epsilon$ 4 genotype (by number of alleles) and by dose level. For participants from the OLE part of the parent studies, only ARIA-E severity measured by the BGTS is available for events that occurred during the OLE part of the parent studies. The timing of ARIA-E and ARIA-H may be summarized by descriptive statistics. Recurrence of ARIA-E within this study or the OLE part of the parent studies will be summarized. ARIA-E with associated and attributable CNS symptoms (see Section 5.3.4.1) and serious associated and attributable CNS symptoms will be summarized overall and also by APOE  $\epsilon$ 4 genotype (by number of alleles). Temporal co-occurrence of ARIA-E and ARIA-H will be summarized overall and also by APOE  $\epsilon$ 4 genotype. Temporal co-occurrence is defined as an MRI scan showing new ARIA-H that occurs between ARIA-E onset and resolution (inclusive), irrespective of the brain region.

MRI findings other than ARIA will also be summarized.

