1.3.2.3 Overall Benefit–Risk Summary

The benefit–risk assessment of gantenerumab treatment in Study WN42171 is based on the following:

- Gantenerumab has shown evidence of continuous reduction of the amyloid plaque component in up to 3 years of treatment and thus shows potential benefit in slowing the progression of AD.
- Findings from Study WN25203 (Klein et al. 2019), the PRIME study with aducanumab (Sevigny et al. 2016), and from the Phase II study with BAN2401 (Swanson et al. 2018) suggest that reduction in deposited amyloid is associated with a dose-related slowing of cognitive decline, providing additional support for the hypothesis that anti-amyloid treatment may be associated with a beneficial clinical effect.
- Results from the double-blind part of Studies WN25203 and WN28745, as well as from the *completed* OLEs Studies WN25203 and WN28745, showed that ARIA-E findings are mostly asymptomatic, non-serious, of mild severity, and do not require permanent cessation of treatment.
- No new safety signals have been identified from the ongoing Phase III studies with gantenerumab with doses of up to 510 mg Q2W or equivalent, which supports the safety of continued administration of gantenerumab uptitrated to the target dose in the current and planned studies, including Study WN42171.
- Study WN42171 will provide participants with the opportunity to extend treatment with gantenerumab beyond 2 years, thereby providing more information on the long-term safety, tolerability, and efficacy of gantenerumab in AD. Furthermore, the study will increase the overall number of participants exposed to gantenerumab and the patient-years of exposure and increase the understanding of the safety:efficacy profile. Analyzing the long-term safety, tolerability, and efficacy of gantenerumab is of critical importance to help clinicians make informed therapeutic decisions for participants.
- The design of Study WN42171 will allow participants with moderate asymptomatic ARIA-E and with any number of ARIA-H microhemorrhages to continue gantenerumab treatment. This is in line with the evolving understanding of the clinical significance of ARIA by the clinical trial Sponsors and medical community (see Section 3.3.4).

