#### 5.3 PRIMARY ENDPOINTS ANALYSIS

### 5.3.1 Definition of Primary Endpoints

The primary objective for this study is to evaluate the safety and tolerability of long-term gantenerumab administered by SC injection on the basis of adverse events (AEs), physical examinations, vital signs, ECGs, laboratory tests, C-SSRS, ARIA-E and ARIA-H, ISRs, treatment discontinuations for AEs, and incidence of AEs of special interest.

The corresponding primary endpoints are:

- Nature, frequency, severity, timing, and outcomes of adverse events and serious adverse events
- Physical examinations (including neurologic systems), vital signs, ECG, laboratory tests, and Columbia-Suicide Severity Rating Scale (C-SSRS)
- Nature, frequency, severity, and timing of ARIA-E and ARIA-H

- Nature, frequency, severity, timing, and outcomes of ISRs
- Incidence of treatment discontinuations for adverse events
- Incidence of adverse events of special interest

The analytical approaches are described in pertinent subsection for each endpoint below.

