### 5.7.2 Summaries of Demographics and Baseline Characteristics

Demographic and baseline characteristics (such as age, sex, race, disease stage at enrolment in the parent studies, stratification factors as reported in IxRS at randomization in the parent studies, APOEe4 status (carrier vs non-carriers and APOe4 allele's status), presence and cumulative number of ARIA-H (during the screening and double-blind part of the parent studies), history of ARIA-E in the double-blind part of the parent studies, and use and non-use of background therapy for AD at OLE baseline, participation in POSTGRADUATE PET substudies) will be summarized descriptively for the ITT and SE analysis sets.

Descriptive summaries of continuous data will present the mean, standard deviation, median, and minimum and maximum. Descriptive summaries of discrete data will include frequencies expressed in terms of number and percentage of participants.

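### ARIA-H severity is in the primary endpoint, but SAP 5.3.4 plans no MRI-based severity or burden summary for it and does not define ARIA-H events against the OLE baseline scan

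*SAP*

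**What the plan says.** Protocol 2.1.1 and SAP 5.3.1 list the same primary endpoint component: "Nature, frequency, severity, and timing of ARIA-E and ARIA-H". Severity is named for both kinds of finding.

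SAP 5.3.4 bases the ARIA analysis mainly on MRI findings. For ARIA-E it plans incidence, "severity (based on the Bioclinica severity scale (see Appendix 2) and the Barkhof Grand Total Score [BGTS]) and timing of ARIA-E". For ARIA-H, "the incidence and timing of ARIA-H will be summarized overall", with breakdowns by APOE ε4 and dose level. SAP Appendix 2 sets out a severity scale for ARIA-E only.

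The counting rule in the same section is "ARIA analyses will be restricted to ARIAs documented during this study or the OLE part of the parent studies". The only place where that section requires ARIA-H to be new is the co-occurrence rule: "Temporal co-occurrence is defined as an MRI scan showing new ARIA-H that occurs between ARIA-E onset and resolution (inclusive".

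Two other places bear on the point. Protocol 1.3.2.3 says the design lets participants "with any number of ARIA-H microhemorrhages to continue gantenerumab treatment". SAP 5.7.2 tabulates, as a baseline characteristic, "presence and cumulative number of ARIA-H (during the screening and double-blind part of the parent studies".

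**The concern.** This study relaxes the handling of ARIA-H. Protocol 1.3.2.1 describes a cumulative count that led to stopping treatment, raised across earlier gantenerumab studies from 5 to 10 to 15. Here no microhemorrhage count does so. Protocol 1.3.2.1 and SAP 1.2.4 both say the sponsor wants to learn whether treatment is safe with more microhemorrhages. That is a question about how many lesions accumulate. A summary of whether and when ARIA-H occurred does not carry that information.

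The counting rule raises a second, smaller question. Participants can enter with existing ARIA-H. SAP 1.2.4 says parent-study treatment was stopped above 15 or for disseminated leptomeningeal hemosiderosis, and the hemorrhagic exclusions in protocol 4.1.2 are disseminated hemosiderosis and macrohemorrhage. If a lesion present at OLE baseline were counted because an OLE scan documents it again, incidence would mix old and new findings. Its timing would then be the first OLE scan, and a prior-placebo participant's old lesion could be placed under the first OLE dose level.

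**Working it through.** The plan states no figure to reproduce. The study is descriptive, and neither document gives an ARIA-H rate. The check is a comparison of sections.

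**Severity**

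1. Endpoint: nature, frequency, severity and timing, for ARIA-E and ARIA-H (protocol 2.1.1, SAP 5.3.1).
2. MRI summaries planned for ARIA-E: incidence, severity on two scales, timing, recurrence.
3. MRI summaries planned for ARIA-H: incidence, timing, and co-occurrence with ARIA-E. Severity is absent.
4. Scale: SAP Appendix 2 and protocol Table 2 grade ARIA-E only. Protocol Appendix 2 separates disseminated from non-disseminated leptomeningeal hemosiderosis for management, but this is not used as a severity summary.
5. Declared changes: SAP Appendix 1 mentions the restriction to OLE-period data, the descriptive approach and the absence of estimands. It says nothing about ARIA-H severity.
6. Consequence: let n be a participant's number of new lesions. Incidence counts 1 if n ≥ 1 and 0 otherwise, so n = 1 and n = 30 contribute equally.

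**What the adverse event tables recover**

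1. Under protocol 5.3.5.2 an ARIA finding is an adverse event if it is symptomatic ARIA-E, changes study treatment, or is otherwise clinically significant to the investigator.
2. Protocol Appendix 2 continues study drug for ARIA-H without disseminated hemosiderosis.
3. Microhemorrhages alone therefore fail the first criterion and, under the management rule, do not trigger the second. They become adverse events only through the third.
4. Intensity for those events follows protocol Table 3, which grades effect on daily activity and not lesion number.

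**Interim analysis**

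SAP 5.8.1 includes MRI safety findings in the analysis meant to support a potential filing, but drops time to onset and the dose-level breakdown. For ARIA-H this leaves little beyond incidence and co-occurrence.

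**Counting**

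1. SAP 5.3.3 limits adverse event tables to events that start or get worse from the first OLE dose.
2. SAP 5.3.4 has no matching rule for MRI findings; the test is documentation in the period.
3. ARIA-E on the last parent-study scan is an exclusion (protocol 4.1.2), so carry-over mainly concerns ARIA-H.
4. An MRI baseline already exists: SAP 5.1.1 takes the last scan within 6 months of OLE Day 1.
5. If incidence is programmed as new or increased findings against that scan, carry-over is zero. If any ARIA-H seen counts, carry-over equals whatever was already present and still visible, for which the documents give no value.

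**The case against.** The sentence on documented ARIA can fairly be read as an exclusion whose purpose is to keep double-blind findings out. The words incidence and timing, the term new in the co-occurrence rule, the separate tabulation of pre-OLE ARIA-H in SAP 5.7.2, and the central reader's duty to flag new MRI findings (SAP 1.2.2) all point to new events. The derivation may also sit in the Data Analysis Plan modules that SAP section 1 mentions and that are not available here. This largely stands. A reader might infer that persisting double-blind lesions do count as OLE events and that prior-active incidence is therefore inflated. The documents do not support that. They never say old lesions count, give no ARIA-H rate at OLE baseline by group, and do not state outright that lesions stay visible, although cumulative counting is consistent with it. What remains is a missing definition.

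On severity, it can be said that ARIA adverse events are reported by intensity, that disseminated hemosiderosis leads to discontinuation and so is captured, and that SAP 5.7.2 gives the cumulative ARIA-H number at entry. So it would be too strong to say ARIA-H severity is summarised nowhere. But these routes cover a selected subset, the extreme case, and the period before the OLE. None describes lesion burden accumulating during open-label treatment. The choice of which endpoint components to summarise belongs in the SAP, so the separate programming documents do not answer this part.

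**Conclusion.** The severity gap holds. One named component of the primary safety endpoint, MRI-based ARIA-H severity, has no planned summary, no measure and no declared omission. As written, the plan cannot describe lesion burden in the OLE period, so it cannot address the stated aim of examining treatment with an increased number of microhemorrhages. This rests on the text alone and needs no assumed rate.

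The counting point is secondary. SAP 5.3.4 does not define ARIA-H incidence against the OLE baseline MRI, so its wording could admit findings carried over from the double-blind part, though the surrounding text suggests otherwise. No size is given because the documents supply no input for one; under the likelier reading it is zero.

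Both should be settled in the SAP before the ARIA tables are produced. Neither affects a hypothesis test, since none is planned.

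**What to change.** In SAP 5.3.4:

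- Add an MRI-based ARIA-H severity summary: the number of new microhemorrhages and the number of new leptomeningeal hemosiderosis foci since the OLE baseline MRI, by previous treatment, parent-OLE participation and APOE ε4. The descriptive statistics in SAP 5.1 suffice, so no cut points are needed.
- State that ARIA-H incidence means new or increased findings compared with the OLE baseline MRI defined in SAP 5.1.1, with onset at the first scan that shows the increase.

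If the sponsor decides against a burden summary, SAP Appendix 1 should say so and why. That would make the omission visible but would leave the aim unaddressed.

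The cost is one amended SAP section, a derived variable and a few tables. All scans are already read centrally, and foci must be counted to apply the definition of disseminated hemosiderosis (more than three, cumulatively). One thing to confirm first: the documents do not say outright that each OLE-period read records the microhemorrhage number, although SAP 5.7.2 relies on such a number from the parent studies.
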